AME00102985: After completing the baseline interview, we will send a letter to control participants that thanks them for their participation in the study and reiterates that we will be contacting them for a follow-up interview in two months. Along with this letter, we will send the Detroit resource lists (including mental health providers and other community resources) that are found on pp 83-86 of the participant manual. The reason for this is that these materials are not directly related to the intervention but participants may find them helpful, especially given that this study is taking place during the pandemic period. Between the baseline and follow-up surveys, participants in the control condition will not take part in any study activities. After completing the follow-up telephone survey, control group members will be given full access to the online program, a wearable physical activity tracker to use and keep, and will be invited to attend a one-time 2.5-hour in-person workshop that summarizes intervention content and that will be led jointly by study staff and a community health worker.

***AME00101151: To accommodate social distancing guidelines, this in-person group workshop may be replaced with a one-hour 1:1 telephone session with a community health worker.

Managing and Protecting Data

Aim 1 Focus Groups and Usability Testing: Potential and confirmed participants' names and contact information (for mailing reminder letters and Human Subjects Incentive Payment cards) will be stored in REDCap and/or a password-protected Excel spreadsheet on a secure University of Michigan School of Public Health server, accessible only to pre-approved study staff and research assistants.

All audio files and transcripts associated with focus groups and usability testing sessions will be stored on a secure University of Michigan School of Public Health server. No names or other identifying information will be included in the transcribed focus group discussions, and thus no information will be included in any published or unpublished reports using interview data that could be used to identify any participant.

Participants' names will not be included on the short supplemental written survey given before the focus groups; these will be anonymous.

Aim 2: Randomized pilot trial: All study participant information will be collected, stored and managed by trained study staff and research assistants in REDCap. REDCap is a secure, web-based application designed to support data capture for research studies, providing 1) an intuitive interface for validated data entry; 2) audit trails for tracking data manipulation and export procedures; 3) automated export procedures for seamless data downloads to common statistical packages; and 4) procedures for importing data from external sources. It is HIPAA compliant and supported by the University of Michigan. This secure web application promotes high quality data collection; forced responses ensure that interviewers are not able to proceed with the survey if required data are missing; and each survey is designed so that only valid responses are entered. For open-ended questions, we will produce coding manuals with detailed instructions for issues such as how to adjudicate coding decisions when survey response options are unclear. A coding-decisions log will be maintained to ensure that coding is consistent.

Electronic data security: Secure servers (virtual machines) at Michigan Medicine will host the SMS platform, store the participants' contact data and responses, and send out SMS messages to participants, who choose this option for reporting daily step counts during the Aim 2 intervention period. Information stored about the participants includes first and last name, a telephone number, and a study ID. We understand that SMS is inherently unsecure; to mitigate this, we will only collect step counts, and we will not use identifying language in the SMS questions asking for step count reports.

Pertaining to Both Aims 1 and 2

Remote Access: Staff is discouraged from accessing electronic files from offsite locations. However, when it is necessary, all connections from remote locations must use the University-configured Cisco VPN client, which encrypts all traffic to and from the servers.

On-site Access and Control: Users are instructed to lock their workstation and to never leave it unattended with an active desktop. This enables access control by allowing only the credentials of the validated user to unlock the workstation. This is especially true when a user is accessing study data.

All databases will be maintained in access-restricted files throughout the study. Study personnel who leave the research team will have their access to study files revoked.

The only paper records with identifiers will be the informed consent documents, and these will be kept in a locked office, in locked file cabinets in the University of Michigan School of Public Health. Access to the file cabinets will be restricted.

Measures.

Telephone surveys will be administered at baseline and 8 weeks from baseline by research assistants not involved in intervention delivery. We will assess all primary and secondary outcomes at both time points. Covariates that are not expected to change over time will only be asked at baseline.

Primary outcomes: Pain interference and physical functioning, which are subscales on the NIH PROMIS-29 Adult Profile Instrument.

Secondary outcomes and/or potential mechanisms of effect will include: physical activity (Physical Activity Scale for the Elderly), Connor-Davidson Resilience Scale, Pain Self-Efficacy Scale, depression, anxiety, social participation (PROMIS) and support (PROMIS), pain catastrophizing, positive/negative affect balance (I-PANAS-SF), life satisfaction, Patient Global Perception of Change.

Covariates/moderators: We will collect data on biological variables that may moderate outcomes, including age, sex, self-reported weight, and comorbidities. Other measures that will be included in one or both surveys include: educational attainment, health literacy, cognitive functioning, pain treatments including use of opioids and other medications, and pain centralization.

Process measures. Program engagement will be indicated by the number of completed CHW sessions, use of web modules, and participant satisfaction. We will use a structured form to evaluate 20% of recorded CHW sessions for fidelity to the intervention protocol.

Post-program qualitative interviews: We will invite participants to take part in an in-depth, semi-structured interview to deepen our understanding of their program experience. These interviews, lasting about 20 minutes each, will be conducted by phone by study staff not involved in intervention delivery, and will consist of open-ended questions about challenges, facilitators, and satisfaction with various aspects of the program and its implementation.

***AME00101151: We are no longer going to be conducting separate qualitative “participant experience” interviews. Instead, we are adding a module with open and close ended questions about program satisfaction to the standard follow-up interviews.

Sample size:

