Procedure: During meetings with the CHWs we will elicit ideas about topics planned for *Positive STEPS* in community-relevant and culturally sensitive ways. CHWs will give feedback on drafts of program protocols and materials, with attention to feasibility of program delivery, relevance and perceived usefulness of content, and use of effective communication strategies for the priority client population. In a final CHW meeting, the CHWs will review participant-facing program refinements (based on focus group feedback, see Aim 1b), as an additional verification of fit. During this final meeting, we will also seek CHW input on a CHW training protocol for the program. We anticipate that this training will use an active learning approach, focusing on skill building and core processes of care, including record keeping and managing referrals for acute events (Patel, Chowdhary, Rahman, & Verdeli, 2011). Meetings will be audio-recorded to facilitate using the information to guide changes to program components.

C3. Aims 1b and 2 Recruitment and Procedure: (**NOTE: These Aims DO include Human Subjects**)

Participant eligibility criteria for both Aims 1 and 2 are as follows:

- *Inclusion criteria:*
 - English-proficient
 - Age \geq 60 years
 - Ambulatory with or without assistive device
 - Community-living
 - Have a cell or landline phone
 - Have Internet access (home or elsewhere);
 - Self-reported chronic musculoskeletal pain (pain in muscles or joints for \geq 3 months); \geq 4 (0-10 scale) average pain level over last week; \geq 1 day/previous 30 when pain made it difficult to do usual activities.

- *Exclusion criteria:*

- Serious acute illness or hospitalization in last month
- Planned surgery in next three months
- Severe cognitive impairment or other severe physical or psychiatric disorder judged by study team to pose significant barrier to deriving program benefit

Aim 1: Focus groups and usability testing for program materials adaptation

Recruitment method 1A: Flyers advertising groups will be displayed or distributed at community locations in Detroit serving older adults.

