Participants assigned to the intervention group will meet with a community health worker (CHW) for a one-hour in-person study orientation session at the UM Detroit Center or location of the participant's choosing. At this session, they will be introduced to the program and choose a day and time for future weekly telephone sessions with the CHW. The CHW will instruct each participant in how to use the web-based modules and worksheets between telephone sessions. Note that the website is only used as a place where participants can access content (videos, text and worksheets); they will NOT be uploading or otherwise inputting any information into the site. The site will be publicly-available; that is, no login will be required. Participants will also be given a wearable physical activity tracker at the orientation session to use throughout the course of the program. The program will be delivered over 6 weeks.

***AME00101151: If social distancing guidelines are in place, the orientation will take place over the phone and all program materials will be mailed.

Each week participants will complete a web-based module with associated handouts, and have one telephone session, of approximately 30 minutes in duration. These sessions will be designed to support the content in a given weekly module (see Table 1). CHWs will elicit problem areas related to the weekly topic, reinforce key points, help participants practice new skills, discuss adaptations needed for a participant's situation, and set a related goal. Participants will also set goals each week related to walking (step counts), a process which will be facilitated by the availability of step-count data from the physical activity tracker. The CHW manual will explain how to interpret and use step-count data in sessions. CHWs will also be trained to provide basic technical support to participants for problems that arise with the website or physical activity trackers.

Table 1. Program modules and role of CHW in supporting module content

Web Module	Content	Type of CHW contact	Role of CHW
------------	---------	---------------------	-------------

Program overview	Chronic pain overview, how symptoms interfere with function, goal setting	No phone call (covered in initial orientation session)	Guide participant in setting long- and short- term behavioral goals, show how to use web modules and workbook.

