Being Active	The role of physical activity, how realistic goals can help maintain exercise over time.	CHW Call 1	Discuss physical activity options and resources in Detroit.
Pleasant Activity Scheduling	Rationale and skills for allocating time to self-growth and well-being.	CHW Call 2	Discuss pleasant activities selected by participant and barriers; set goal.
Reminiscence and Meaning-Making	Looking back on one's life and reflect on positive moments.	CHW Call 3	Discuss how to select positive life moments and plan for recording (optional): written, video, etc.
Participant choice: Acts of Kindness, Positive Piggy Bank, or Savoring	Participant will be introduced to several positive affect-inducing activities and will choose one to try.	CHW Call 4	Discuss which resilience-based activities (legacy/life story, gratitude, etc.) is most appealing; set goal. (e.g., savoring – guide participant in choosing two everyday experiences to savor each day)
Music as Medicine	Rationale and activities for using music for pain management.	CHW Call 5	Develop plan to incorporate listening to music (of participant's choice) for an hour on at least five days with minimal distraction.
Wrap-up	Review of key skills and relapse prevention strategies.	CHW Call 6	Guide participant in developing plans to continue goal completion.

More details about intervention content:

Note that we are not requiring that participants secure their doctor's approval for physical activity prior to program participation, given that the CHWs will not ask participants to engage in anything more than moderate walking activity. The suggested amount of walking will start out at or close to a participant's usual amount of walking (as measured by daily step counts) and CHWs will encourage participants to increase their daily steps only very gradually (e.g., by 10% per week).

In the event of patients reporting serious depressive symptoms or suicidal ideation, the CHW will follow an established protocol, used in our other studies, which will include notifying the PI, providing a suicide hotline number, and calling 911 if needed. *Quality assurance* for CHW-delivered sessions will include: (1) observation by the PI or Co-I of several telephone sessions; (2) review by the PI or Co-I of CHW clinical records; and (3) weekly meetings with CHWs consisting of reinforcement of training and case reviews.

More details about activity tracker and how it will be used in the intervention:

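### Weekly walking goals rise without required medical clearance, yet no listed measure or planned analysis counts falls, injuries, urgent care or transient pain flares in either arm

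*Combined protocol and SAP*

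**What the plan says.** **Activity component.** Under Intervention Condition, "Participants will also set goals each week related to walking (step counts"). Under More details about intervention content, the protocol states that "we are not requiring that participants secure their doctor's approval for physical activity prior to program participation". The reason it offers is a limit on what will be requested: "given that the CHWs will not ask participants to engage in anything more than moderate walking activity". It adds that "The suggested amount of walking will start out at or close to a participant's usual amount of walking", and that CHWs will encourage participants to "increase their daily steps only very gradually (e.g., by 10% per week"). In Table 1, the CHW's role in Call 1 (Being Active) is worded more widely: "Discuss physical activity options and resources in Detroit".

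**Population.** Section C3 admits people aged 60 or older who walk with or without an assistive device and whose average pain over the last week is at least 4 on a 0–10 scale. It excludes recent serious acute illness or hospitalization and surgery planned within three months. It also excludes severe cognitive impairment or other severe disorder "judged by study team to pose significant barrier to deriving program benefit".

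**Measurement.** Measures sets telephone surveys at baseline and 8 weeks. The primary outcomes are pain interference and physical functioning, and Patient Global Perception of Change is among the secondary measures. On process, "Program engagement will be indicated by the number of completed CHW sessions, use of web modules, and participant satisfaction", together with a fidelity review of 20% of recorded sessions. The Statistical analysis plan covers regression on the outcomes, mediation, moderation, a responder analysis, effect sizes and sensitivity to missing data. It does not mention harms.

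**Contact by arm.** The intervention arm has an orientation and six CHW calls (Table 1). Under Control Condition, controls receive a letter with resource lists and have no study activities between the two surveys.

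**The concern.** Only one arm is encouraged to walk more, and its members are older adults with at least moderate pain, some of whom use assistive devices. Falls, injuries and short-lived flares are events one would want counted in such a program, and the listed measures count none of them.

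Under Sample size, the pilot's stated purpose is to look for a pattern suggesting promise, and the analysis plan says the results will feed a larger trial. A plan followed exactly as written could report acceptability and promise with no comparable information on physical harm. A later investigator would have no event rate from this population to use in planning.

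Uneven contact adds a second problem. Whatever events did surface would come mostly from people who speak with a CHW every week. An excess of reports in the intervention arm could reflect the program or merely the opportunity to report. A low count could not be read as reassurance, since nobody was asked.

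**Working it through.** The plan states no event rate, power or harms figure, so there is nothing to reproduce. The check is a comparison of sections, followed by arithmetic on what 25 per arm could show.

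**1. Could each listed item register a discrete event?**
- Pain interference and physical functioning (primary, both arms, 8 weeks): these can show worsening that is still present at the survey. They cannot identify a fall, an injury or a flare that has resolved.
- Patient Global Perception of Change: an overall judgment, with the same limit.
- Other secondary measures, covariates and moderators: none is described as a fall, injury, urgent-care or flare item.
- Process measures: sessions completed, module use, satisfaction and fidelity. None records harm.
- Satisfaction module added to the follow-up interview by amendment: it concerns the program, which controls have not yet received.
- Statistical analysis plan: no harms summary or comparison.

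**2. Which routes could carry a volunteered event?**
- Complaints or concerns voiced to staff go to the PI (both privacy sections of the protocol). This is open to both arms but depends on someone raising the matter.
- CHW records, reviewed by the PI or a co-investigator, and weekly case reviews: intervention arm only.
- Anticipated CHW training on record keeping and acute-event referrals (section C2): intervention arm only.
- CHW calls explore problems with the weekly topic and needed adaptations: intervention arm only, and not a fixed harms question.
- The CHW event response set out under More details about intervention content is for serious depressive symptoms or suicidal ideation.

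Opportunities to volunteer an event on a scheduled call between the surveys are therefore up to 6 in the intervention arm and 0 in the control arm.

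**3. What would identical 8-week items show?** Inputs: n = 25 per arm (Plan for Assignment of Participants). Full follow-up is assumed. The event risks p are also assumptions, because the documents give none.

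Chance of at least one event in an arm = 1 − (1 − p)^25:
- p = 2%: 1 − 0.98^25 = 39.7%
- p = 5%: 1 − 0.95^25 = 72.3%
- p = 10%: 1 − 0.90^25 = 92.8%
- p = 20%: 1 − 0.80^25 = 99.6%

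Exact one-sided 95% upper bound after 0 of 25 = 1 − 0.05^(1/25) = 11.3%.

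Approximate power to compare arms, two-sided 5% = Φ[(|p1 − p2| − 1.96·s0)/s1]. Here s0 = √(2p̄(1 − p̄)/25), p̄ is the mean of p1 and p2, and s1 = √(p1(1 − p1)/25 + p2(1 − p2)/25):
- 5% v 10%: 9.8%
- 5% v 20%: 35.7%
- 10% v 30%: s0 = √(2 × 0.20 × 0.80/25) = 0.1131 and s1 = √((0.09 + 0.21)/25) = 0.1095, so Φ[(0.20 − 0.2217)/0.1095] = 42.1%

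Events of moderate frequency would probably be seen if asked about. A between-arm test would be uninformative.

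**The case against.** The best reply is that harm would not be invisible. Both primary outcomes and the global-change measure are taken in both arms at 8 weeks, and staff have routes by which a reported event reaches the PI. The walking component is cautious, with a start near usual activity, very gradual increases, and exclusions for recent acute illness, hospitalization and planned surgery. All of this stands. It limits the point to systematic counting and comparability by arm, but does not supply either.

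Three stronger readings are tempting, and the documents do not support them.

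- *Harm from the step increases would go unseen.* Lasting deterioration would appear in the 8-week outcomes, and volunteered events can reach the PI.
- *Table 1 breaks the walking-only rationale.* The rationale concerns what CHWs ask participants to do, whereas Call 1 has them discuss options. Discussion is not a request for more than moderate walking. The wording is in tension, but it is not a flat contradiction.
- *Steps will rise by 60% or more.* If the 10% example were taken up every week and compounded, five increases would give 1.10^5 = 1.61 times the starting level and six would give 1.10^6 = 1.77. The rate is only an example, CHWs only encourage, and the number of increases is not stated. These figures are a ceiling under assumptions, not a planned dose.

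The survey instruments and CHW manual are not among the documents, and the consent pages were removed. Harm items could exist there, so the point is about listed measures only.

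**Conclusion.** The point holds in limited form. As documented, the plan encourages rising step counts in one arm without requiring a doctor's approval. It lists no measure and plans no analysis that counts falls, injuries, urgent care or transient pain flares in either arm. Ad hoc reports could not fill the gap because contact between surveys is unequal.

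The consequence is absent descriptive safety information for up to 50 participants, 25 per arm. It does not bias the stated outcomes. Even when collected, the counts could not exclude event risks below about 11% when none is observed, and power for the assumed contrasts is 10% to 42%. These figures assume full follow-up and illustrative risks.

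This is a cheap improvement that should be made, not a flaw that invalidates the pilot. No view is taken on whether clearance should be required, how fast steps should rise, or how CHWs should handle events on weekly calls.

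**What to change.** 1. Add one short, fixed set of items to the 8-week telephone survey, worded identically in both arms: falls, injuries, urgent care or hospital use, and pain flares since baseline. If the survey forms already contain such items, list them under Measures.
2. Add a sentence to the Statistical analysis plan: the number and percentage of participants with each event, and the number of events, will be reported by arm with exact confidence intervals and no hypothesis test. Events volunteered to CHWs or staff at other times should be listed separately and kept out of the between-arm comparison.
3. Separately, reconcile the walking-only rationale under More details about intervention content with the wider wording of Table 1, Call 1, so that both describe the same activity content. Which wording is right is for the sponsor to settle.

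The cost is one amendment and a slightly longer follow-up survey. That interview was already lengthened when the satisfaction module was added, so the set should be kept to a few items. Recall over 8 weeks will miss some minor events, but the recall period is the same in both arms.
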